AEH and EEC patients will be firstly stratified, and then both randomly assigned (1:1) to receive MA treatment (control group) or metformin plus MA treatment (experimental group) until complete regression or disease progression or unacceptable side effects, whichever occurs first. A computer-based procedure of simple randomization (SPSS for Mac, version 20.0; IBM) will be used for participant enrollment and randomization. Before an individual is successfully enrolled, her treatment assignment will remain concealed. This trial will be open label: patients and study physicians were aware of treatment assignment.

Outcomes

The primary end point is the accumulate CR rate within three months of

treatment. The accumulate CR rate within six, nine, twelve months of treatment, time to CR, adverse events, recurrence rate and pregnancy rate in two years are secondary end points.

Statistical analysis

For primary endpoint, a baseline CR rate of 25% in MA group and an expected CR rate of 50% in MA/metformin group were expected according to results in our previous pilot study, with a power of 0.9 at a two-sided significance level of 0.05, requiring an accrual 150 eligible patients (lost follow-up rate <5%). Relapse rate will be calculated among patients who achieved CR. Pregnancy rates will be evaluated among patients who planned to conceive once achieving CR. Continuous variables will be summarized by means and standard deviations, or median and interquartile range (IQR). Categorical variables will be presented as frequency with percentage. The intra-group differences of continuous variables will be investigated by Student's t-test or Mann-Whitney U test where appropriate. Chi-square test or Fisher's exact test will be used to analyze the difference between categorical variables. Adjusted Odds ratios (OR) and 95% CI will be estimated with Logistic regression model. Estimates of time to CR will be calculated using the Kaplan-Meier method. A 2-tailed p value of less than 0.05 will be considered as statistically significant. SPSS 20.0 (SPSS, Inc., Chicago, IL, USA) will be used for all the statistical analyses.

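### Does an accrual of 150 miss the stated 0.9 power because it leaves no room for the loss to follow-up named beside it?

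*Combined protocol and SAP*

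**What the plan says.** The sample size appears once, in the Statistical analysis section of the synopsis. The assumed rates are "a baseline CR rate of 25% in MA group and an expected CR rate of 50% in MA/metformin group were expected", and the design claim is "with a power of 0.9 at a two-sided significance level of 0.05, requiring an accrual 150 eligible patients (lost follow-up rate <5"%). Allocation is given under Randomization and masking: AEH and EEC patients are stratified, then "both randomly assigned (1:1) to receive MA treatment (control group) or metformin plus MA treatment (experimental group"), by simple randomization. The primary endpoint, under Outcomes, is cumulative CR within three months; secondary endpoints extend to two years.

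For categorical comparisons the plan offers a chi-square test or Fisher's "exact test will be used to analyze the difference between categorical variables", and assigns neither to the primary endpoint by name. The significance rule is "A 2-tailed p value of less than 0.05 will be considered as statistically significant".

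The plan does not name the sample-size formula, give a number of evaluable patients, show an inflation step, or say how patients lost before three months are counted.

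**The concern.** Power, accrual and loss stand in one sentence, so a reader may take 150 as the number that delivers 90% power after loss of up to 5%. Sample-size statements usually work that way: compute the evaluable number, then divide by one minus the loss. Here 150 lies between the two common no-loss answers, which suggests that no such division was made. If so, the trial would run slightly below its advertised power whenever loss neared the ceiling, and nobody could tell which evaluable number the 0.9 refers to. At stake would be an overstated power or a recruitment target 6 to 12 patients too low.

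**Working it through.** **Inputs**, all from the Statistical analysis and Randomization sections: control CR rate 0.25 ("a baseline CR rate of 25% in MA group"), experimental CR rate 0.50 ("an expected CR rate of 50% in MA/metformin group"), power 0.90 ("with a power of 0.9"), two-sided alpha 0.05, 1:1 allocation, 150 accrued, loss below 5%. The normal quantiles are 1.96 and 1.2816, the difference is 0.25, and the mean rate is 0.375.

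**Step 1: reproduce 150 without loss.**

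- Unpooled variance: (1.96 + 1.2816)² × (0.1875 + 0.25) / 0.0625 = 73.55, so 74 per arm, 148 in total.
- Pooled variance: (1.96 × √(2 × 0.375 × 0.625) + 1.2816 × √(0.1875 + 0.25))² / 0.0625 = 76.71, so 77 per arm, 154 in total.
- Arcsine: 76.65, so also 154.

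The stated 150 lies within this range, four below its top and two above its bottom. It reproduces.

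**Step 2: accrual that would cover a full 5% loss.**

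- Unpooled: 73.55 / 0.95 = 77.4, so 78 per arm, 156 in total.
- Pooled, rounded once: 76.71 / 0.95 = 80.7, so 81 per arm, 162 in total.

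Neither gives 150. A smaller loss does: with the unpooled formula and 1% loss, 73.55 / 0.99 = 74.3, so 75 per arm and exactly 150. That fits both the two-sided test and a loss below 5%, although it is only one possible origin of the number. A one-sided test at 0.05 with continuity correction also arrives at 150 (71 per arm, 142 / 0.95 = 149.5), but it contradicts the stated two-sided level.

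**Step 3: power that 150 accrued delivers.** Five percent of 150 is 7.5, so a loss below 5% means at most 7 patients, leaving 143 (71 and 72).

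| Evaluable | Pooled | Exact, uncorrected chi-square | Unpooled |
|---|---|---|---|
| 150 (75/75) | 0.893 | 0.897 | 0.906 |
| 148 (74/74) | 0.889 | – | 0.902 |
| 146 (73/73) | 0.885 | 0.886 | 0.898 |
| 143 (71/72 or 72/71) | 0.878 | 0.880 to 0.884 | 0.892 |

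At the ceiling the shortfall from 0.90 is 0.90 − 0.892 = 0.8 points to 0.90 − 0.878 = 2.2 points. The choice between pooled and unpooled formula alone moves power by 0.906 − 0.893 = 1.3 points at 75/75. Every value in the table rounds to 0.9.

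**Step 4: the effect in clinical units.** With 71 per arm, the pooled formula reaches 90% power for 25% against about 51%, instead of 50%.

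**Step 5: other ways of counting loss and other tests.**

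- If 5% are lost and kept in the denominator as non-CR, the rates become 0.2375 and 0.475, and pooled power at 75 per arm is 0.867.
- If Fisher's exact test were used, power would be about 0.864 at 75/75 and 0.854 to 0.863 with 143. A continuity-corrected chi-square would give about 0.844 with 143. The smallest expected cell is about 71 × 0.375 = 26.6, so there is no small-cell reason to leave the ordinary chi-square test.

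**The case for a change.** The strongest case for acting is that the sentence does not close under either reading. If the loss figure is an allowance, 150 is 6 to 12 short. If it is a target for trial conduct, the plan still accepts up to seven losses, and no uncorrected calculation reaches 0.90 there. The unpooled formula, the most favourable, absorbs two losses (0.902 with 148) but not four (0.898 with 146). Pooled and exact power are just under 0.90 with no loss at all. The remedy would be one sentence of wording, and this is the trial's only sample-size statement.

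The arithmetic in that case stands. The inference from it does not. The plan never says that 150 includes a 5% inflation, so no stated calculation has failed. The loss figure is an upper bound, and testing only the bound shows the worst case rather than the expected one. No period is attached to it: if it describes the whole trial, with follow-up to two years, loss by the three-month endpoint would be lower and the shortfall smaller. A precision of one or two points is also finer than a planned power given as 0.9, or than the 25% and 50% planning rates taken from a pilot study.

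The point about the unnamed primary test also has some substance, since Fisher's test would cost about three points. But the plan's wording leaves room for the usual practice of reserving Fisher's test for small expected counts, and the expected counts here are large.

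**Conclusion.** The concern does not call for a change. The accrual of 150 reproduces the stated power of 0.9 for 25% against 50% at two-sided 0.05 with little or no loss. At the highest loss the plan contemplates, power is about 0.88 to 0.89, which the plan's own rounding still prints as 0.9. What remains is missing detail: the formula, the meaning and period of the loss figure, and the evaluable number. Supplying it would leave the recruitment target, the test and the interpretation of the result as they are.

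The conclusion rests on four assumptions: an uncorrected chi-square test for the primary endpoint, lost patients excluded, loss spread about equally over the arms, and arms of nearly equal size. Simple randomization does not guarantee 75/75, but modest imbalance costs little: an illustrative 80/70 split has the precision of 2 / (1/80 + 1/70) = 74.7 per arm under a common variance. If lost patients were counted as non-CR, power at 5% loss would be about 0.867, which also rounds to 0.9.

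### Two-year recurrence and pregnancy are crude proportions with no time origin or censoring rule, so the absolute rates can fall below the 24-month risk after CR

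*Combined protocol and SAP*

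**What the plan says.** The Outcomes section states that "recurrence rate and pregnancy rate in two years are secondary end points". The Statistical analysis section sets the denominators: "Relapse rate will be calculated among patients who achieved CR" and "Pregnancy rates will be evaluated among patients who planned to conceive once achieving CR".

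Kaplan-Meier is named for one end point only, time to CR. Recurrence and pregnancy are rates, so they come under the general rules for categorical data: percentages, chi-square or Fisher's exact test, and adjusted odds ratios from logistic regression.

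The plan does not say whether the two years start at randomisation, at start of treatment or at CR. It gives no minimum follow-up after CR and no rule for women observed for less than two years. The only follow-up figure is the loss rate below 5%, which stands in the sample-size sentence for the primary end point.

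Times of CR vary by design. The secondary end points include "The accumulate CR rate within six, nine, twelve months of treatment, time to CR", and the Randomization and masking section has treatment continue until complete regression, progression or unacceptable side effects.

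**The concern.** A woman can relapse, or start trying to conceive, only after CR. Women therefore enter the risk period at different times, and the trial is built on the expectation that the metformin arm enters sooner: "a baseline CR rate of 25% in MA group and an expected CR rate of 50% in MA/metformin group" at three months. A crude proportion ignores this.

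- **Two years from entry.** A woman with CR at month 3 is observed at risk for 21 months, and one with CR at month 12 for only 12. Time at risk differs between women and, on average, between arms. The result is not the 24-month risk after CR.
- **Two years from CR.** The proportion is sound if every woman is followed for 24 months. If some are not, the result depends on how they are counted, and the plan is silent on that.

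Eligible women wish to preserve fertility, so the two-year chances of relapse and pregnancy are figures on which later patients would be counselled. In an open-label trial, the time origin and the handling of short follow-up should also not be left until the data have been seen.

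**Working it through.** **The plan's own figure.** The plan gives no expected two-year relapse or pregnancy rate, so there is none to reproduce. Its sample size does reproduce. For 25% against 50%, "with a power of 0.9 at a two-sided significance level of 0.05", the unpooled formula gives (1.960 + 1.282)² × (0.25×0.75 + 0.50×0.50) / 0.25² = 73.6, so 74 per arm and 148 in total. The pooled formula gives 154. The plan states 150. This does not bear on the two-year end points.

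**Inputs.** From the plan: CR of 25% and 50% at three months, CR counted at 3, 6, 9 and 12 months, 1:1 allocation of 150 women (75 per arm), loss below 5%. Assumed: the same CR chance h in each later three-month interval among women not yet in CR, and a constant relapse or conception risk after CR that is equal in both arms.

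**Step 1, time to CR.** The weights at months 3, 6, 9 and 12 are h(1−h)^k, k = 0 to 3, normalised over responders.
- MA (h = 0.25): 0.366, 0.274, 0.206, 0.154; mean 6.4 months; 68% in CR by month 12.
- MA plus metformin (h = 0.50): 0.533, 0.267, 0.133, 0.067; mean 5.2 months; 94% in CR by month 12.

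**Step 2, two years from entry.** Time at risk is 24 − t.
- Relapse at an assumed 20% per year: 1 − 0.8^((24−t)/12) is 32.3%, 28.4%, 24.3% and 20.0% for CR at months 3, 6, 9 and 12. The weighted rates are 27.7% (MA) and 29.4% (MA plus metformin). The 24-month risk after CR is 1 − 0.8² = 36.0% in both arms.
- Conception at an assumed 3% per month: 1 − 0.97^(24−t) gives 41.1% and 43.4%, against 1 − 0.97^24 = 51.9%.

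The same calculation over a range of 24-month risks after CR, with CR found at the visits or at any time up to month 12 (exponential):

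| Risk after CR | Visits: MA / MA+metformin | Any time: MA / MA+metformin |
|---|---|---|
| 10% | 7.4% / 7.9% | 8.0% / 8.6% |
| 20% | 15.0% / 16.0% | 16.3% / 17.3% |
| 40% | 31.0% / 32.9% | 33.3% / 35.2% |
| 60% | 48.4% / 50.9% | 51.4% / 53.9% |

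The arms differ by about 0.5 to 2.5 points although the risk after CR is equal.

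**Step 3, two years from CR.**
- All followed for 24 months: the crude rate is unbiased.
- 5% lost at 12 months and counted as event-free: 0.95×0.36 + 0.05×0.20 = 35.2%, which is 0.8 points low.
- 5% lost immediately: 0.95×0.36 = 34.2%, which is 1.8 points low. A true 20% reads 19% and a true 40% reads 38%.
- Common data cut (assumed 36-month accrual, cut 12 months after last entry): only 53% (MA) and 57% (MA plus metformin) of responders have 24 months after CR. A true 20% reads 16.8% and 17.2%; a true 40% reads 34.2% and 34.9%. With the cut 24 months after last entry, a true 40% reads 39.4% and 39.6%.

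**Step 4, distortion against sampling error.** Responders by month 12 are 75 × 0.684 = 51 and 75 × 0.9375 = 70.
- Relapse: SE = √(0.277×0.723/51 + 0.294×0.706/70) = 8.3 points. The 1.7-point distortion is 0.20 SE, and a 5% test would reject about 5.5% of the time.
- Pregnancy, if every responder plans to conceive: 2.3 points against 9.1, or 0.25 SE, with rejection about 5.7% of the time.

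**The case against.** A reader might infer that the crude rates are too low under either time origin, and that the plan would create a false excess of relapse and pregnancy in the metformin arm. The documents do not support this, for four reasons.

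- Counted from CR with complete follow-up, the crude proportion is unbiased. The plan nowhere says that incompletely followed women count as event-free; it simply gives no rule.
- The only loss figure in the plan is below 5%, and at that level the error is about 1 to 2 points. That figure belongs to the primary end point, so it may not cover two years after CR, but the plan gives no higher one.
- Relapse within two years of entry is a legitimate quantity in its own right. The 28% to 29% is not a wrong estimate of it; it is a different quantity from the 36%. For pregnancy, conceiving sooner because CR came sooner can be a real benefit of treatment, which a clock started at CR would remove.
- The difference created between arms is about a fifth to a quarter of a standard error in the worked example.

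All of this stands. It does not settle the matter, because the plan commits neither to an origin nor to complete follow-up. A reader of a published two-year rate could not tell which quantity it was, and would probably take it as the risk after CR.

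A further limit applies to any remedy. Both comparisons are made among women who reached CR, a group formed after randomisation and of different size in each arm. Time-to-event methods do not cure that.

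**Conclusion.** The point holds as a conditional one. Two-year recurrence and pregnancy are crude proportions without a time origin or censoring rule, in a trial where the start of the risk period varies by many months and is expected to differ by arm.

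Counted from entry, the rate falls below the 24-month risk after CR: 28% to 29% against an assumed 36%. Counted from CR, the shortfall is nil with complete follow-up, about 1 to 2 points if 5% are lost and counted as event-free, and about 3 to 6 points under the assumed early data cut. The distortion between arms is about 0.5 to 2.5 points on the from-entry reading and would rarely change a test result.

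The post-CR risks, the accrual period, the data cut and the constant-hazard model are all assumptions; only the three-month CR rates, the assessment times, the sample size and the loss figure come from the plan. These are secondary end points and the primary analysis is unaffected. The change is still worth making, because the absolute rates matter to these patients and the better method is already in the plan for time to CR.

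**What to change.** In the Statistical analysis section:

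1. Measure recurrence from the date of CR, and state the origin for pregnancy as well.
2. Estimate 24-month recurrence and pregnancy by Kaplan-Meier or, with hysterectomy as a competing event, by cumulative incidence. Censor at last contact.
3. Compare the arms with a time-to-event test stratified by AEH/EEC, in place of chi-square or Fisher.
4. Report the length of follow-up after CR by arm.
5. If wanted, report pregnancy within two years of entry alongside, with its origin named, since earlier CR can be a real benefit.
6. Label both comparisons as conditional on CR and so not fully protected by randomisation.

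The cost is mainly SAP wording. Intervals will be slightly wider, the estimates rely on non-informative censoring, and dates of CR, relapse, pregnancy, hysterectomy and last contact must be recorded. The document has no data-collection schedule, so whether those dates are already captured after CR needs checking.

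### Randomisation is stratified by AEH or EEC, but no analysis of 3-month complete response is stated to use the stratum; a stratified test would be a free improvement

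*Combined protocol and SAP*

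**What the plan says.** All of this is in the combined protocol and SAP.

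- **Randomization and masking:** "AEH and EEC patients will be firstly stratified, and then both randomly assigned (1:1"). The method within strata is simple: "A computer-based procedure of simple randomization (SPSS for Mac, version 20.0; IBM) will be used". No blocking is mentioned. The trial is open label.
- **Outcomes:** "The primary end point is the accumulate CR rate within three months of" treatment. CR by 6, 9 and 12 months is secondary.
- **Statistical analysis, sample size:** "a baseline CR rate of 25% in MA group and an expected CR rate of 50% in MA/metformin group", "with a power of 0.9 at a two-sided significance level of 0.05", giving 150 patients.
- **Statistical analysis, tests:** no sentence is devoted to the primary endpoint. Two general sentences could apply: "Chi-square test or Fisher's exact test will be used to analyze the difference between categorical variables" and "Adjusted Odds ratios (OR) and 95% CI will be estimated with Logistic regression model". The first has no stratum. The second lists no covariates and names no endpoint. No stratified test appears anywhere.

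**The concern.** The sponsor thought diagnosis important enough to stratify on, yet the plan does not say that any comparison of CR takes it into account. Read literally, 3-month CR will be compared by a crude chi-square or Fisher test.

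If CR differs between AEH and EEC, two things are lost. The crude comparison carries the between-diagnosis variation as noise, which costs power. It also leaves the estimate uncorrected when the diagnosis mix happens to differ between arms. Stratifying and then using simple randomisation does not force balance within strata, so the analysis is the only place where the stratum can do any work.

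There is also a prespecification problem. With the test and the covariates both open in an open-label trial, the choice among crude chi-square, Fisher and an adjusted model can be made after the results are known.

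**Working it through.** **1. The plan's own sample size.** Inputs from the Statistical analysis section: CR 0.25 and 0.50, power 0.90, two-sided 0.05.

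- Unpooled variance: n per arm = (1.960 + 1.282)² × (0.25×0.75 + 0.50×0.50) / 0.25² = 10.51 × 0.4375 / 0.0625 = 73.6, so 74 per arm, 148 in total.
- Pooled variance: 77 per arm, 154 in total.
- Power at 75 per arm (normal approximation): Φ[(0.25×√75 − 1.960×√(2×0.375×0.625)) / √0.4375] = Φ(1.24) = 0.893.

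So 150 is reproduced, before any allowance for loss, as a crude two-proportion calculation.

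**2. Assumptions.** The documents do not give the AEH/EEC mix or CR by diagnosis. Assumed: EEC share w of 20%, 30% or 50%; CR lower in EEC than in AEH by a gap g of 0, 10, 20 or 30 points; overall CR fixed at 25% and 50%; all 150 patients evaluated; simple 1:1 allocation within strata, as the plan describes.

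**3. Where a gain comes from.** In each arm the crude variance includes a between-diagnosis part, w(1−w)g². At w = 50% and g = 30 points this is 0.25 × 0.09 = 0.0225 per arm. The variance sum falls from 0.4375 to 0.4375 − 2×0.0225 = 0.3925, a ratio of 1.11. In simulation the SD of the difference was 0.0767 crude and 0.0729 Mantel-Haenszel, also a variance ratio of 1.11. At g = 0 the ratio is 0.99.

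**4. Power.** Simulation, 200,000 trials per scenario, same gap in both arms. With a_k responders among t_k experimental patients, c_k controls, m_k responders in total and N_k patients in stratum k, the test was CMH = [Σ(a_k − t_k m_k/N_k)]² / Σ[t_k c_k m_k(N_k − m_k)/(N_k²(N_k − 1))], against uncorrected Pearson chi-square. Change in power (CMH minus Pearson), in percentage points:

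| EEC share | gap 0 | gap 10 | gap 20 | gap 30 |
|---|---|---|---|---|
| 20% | −0.3 | −0.1 | +0.6 | +1.6 |
| 30% | −0.3 | −0.1 | +0.9 | +2.3 |
| 50% | −0.3 | 0.0 | +1.1 | +2.8 |

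Pearson power is 0.892 to 0.894 throughout; CMH runs from 0.889 to 0.921. If instead the odds ratio is the same in both strata (gap defined in the control arm), the change is about −0.3, +0.1, +1.2 to +1.6, and +3.7 to +4.4 points.

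**5. Type I error.** With CR 25% in both arms and simple allocation: crude 0.050 to 0.051, CMH 0.049 to 0.050. The crude test would be conservative only under balanced allocation within strata (0.043 to 0.046 at a 20-point gap, 0.037 to 0.041 at 30), which the plan does not describe.

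**6. Chance imbalance.** With about 75 per arm, the SD of the between-arm difference in EEC share is √[w(1−w)×2/75] = 0.065, 0.075 and 0.082 for w = 20%, 30% and 50%. A difference of 10 points or more then occurs in 13%, 18% and 22% of trials. At w = 50%, in the 11% of trials where the experimental arm has at least 10 points more EEC, the crude difference averages 23.6, 22.2 and 20.8 points (gaps 10, 20, 30) against a true 25. The Mantel-Haenszel difference averages 25.0.

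**7. Which version of the test.** A continuity-corrected CMH has power 0.853 to 0.890, which is 3.0 to 3.6 points below the uncorrected version and below Pearson in every scenario. The plan's own choice also matters: at exactly 75 per arm, exact power is 0.897 for uncorrected Pearson and 0.863 for Fisher, a difference of 3.4 points.

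**The case against.** The strongest reply is that the planned logistic model may well include diagnosis: CR is the obvious binary outcome and the stratification factor an obvious covariate. The plan does not exclude that, but it does not state it either. The defensible claim is therefore that no analysis is stated to use the stratum, not that none will.

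Next, the crude test is valid and unbiased over repeated trials, and the gain is nil or slightly negative at gaps of 0 to 10 points. That stands. So does the remark that the largest gains need extreme inputs. Keeping control CR at 25% overall with a 30-point gap implies control CR in EEC of 0.25 − (1−w)×0.30, that is 1%, 4% or 10% at EEC shares of 20%, 30% and 50%.

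The imbalance example is a selected tail. Imbalance the other way is equally likely, and a shift of 1.4 to 4.2 points compares with a standard error of about 7.7. That is fair, and it is why the point is about conditional precision and not bias.

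Finally, CMH is not the only remedy, and it can lower power if run with a continuity correction. Both are true, and the fix allows for them. None of this is a reason to leave the test and the covariates open.

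**Conclusion.** The concern holds as a free improvement, not as a validity error. Randomisation is stratified by diagnosis, the only test that fits the primary endpoint is unstratified, and the adjusted model is not tied to the stratum or to 3-month CR.

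For power, the stake runs from a loss of about 0.3 points if diagnosis does not predict CR to a gain of about 1 point at a 20-point gap and 1.6 to 4.4 points at 30 points. The range reflects the assumed mix and whether the effect is constant as a risk difference or as an odds ratio. The documents support no particular value within it. Protection against chance imbalance and a single prespecified primary analysis are worth having even where the power gain is negligible. The change should be made; confidence in the size of the benefit is moderate.

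**What to change.** In the Statistical analysis section, name one primary analysis of 3-month CR: a CMH test stratified by AEH/EEC, explicitly without continuity correction, with a stratum-adjusted estimate and 95% CI, for example the Mantel-Haenszel risk difference. Apply the same stratification to CR by 6, 9 and 12 months. List AEH/EEC as a covariate in the logistic models and state which endpoints they serve. Keep the crude chi-square as a sensitivity analysis. A logistic model for 3-month CR with AEH/EEC as a prespecified covariate, declared primary, would also close the gap.

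The cost is wording. Diagnosis is known for every patient before randomisation, the sample size stays at 150, and the worst case is about 0.3 points of power. The plan names SPSS 20.0 for all analyses, so confirm that its output gives the uncorrected statistic and the chosen interval. If it does not, both can be computed directly from the two 2×2 tables.

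### Time to CR is estimated by Kaplan-Meier with no rule for women who progress or stop for side effects; if they are censored at that point, the curve overstates cumulative CR in each arm

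*Combined protocol and SAP*

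**What the plan says.** Under Randomization and masking, study treatment continues "until complete regression or disease progression or unacceptable side effects, whichever occurs first". Two of these three endings are endings without CR.

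Under Outcomes, the primary end point is the cumulative CR rate at three months (the sentence opens "The primary end point is the accumulate CR rate within three months of"). Time to CR is secondary. It is listed beside the later cumulative CR rates, in the sentence that begins "The accumulate CR rate within six, nine, twelve months of treatment, time to CR, adverse events, recurrence rate and pregnancy rate in two years are".

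Under Statistical analysis, the method for time to CR is one sentence: "Estimates of time to CR will be calculated using the Kaplan-Meier method". For categorical variables the plan states that "Chi-square test or Fisher's exact test will be used to analyze the difference between categorical variables", and it adds logistic regression for adjusted odds ratios.

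The plan gives no censoring rule for time to CR, no competing-event method, no rule on assessment after treatment stops, and no between-arm test for this end point. It defines denominators for relapse and pregnancy but none for the CR rates.

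**The concern.** A censored woman is assumed to have the same later chance of the event as women still at risk. That is hard to defend for a woman censored because her disease progressed. It is also doubtful for a woman who stops for side effects, since the trial is open label and decisions to stop are made knowing the arm.

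If such women are censored at the stop, the curve describes how fast CR would come if nobody progressed or stopped. It does not describe the proportion of randomized women who reach CR by a given month. Two things are at stake:

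- The CR probability read from the curve would be too high in each arm, by amounts that can differ between arms.
- The trial could report two different CR figures for month 6, 9 or 12: one from the curve and one from the cumulative rates, if the latter count stopped women as non-responders.

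**Working it through.** **The plan's own figure.** The plan states no number for time to CR. Its one design figure is 150 women for the 3-month rate: "a baseline CR rate of 25% in MA group", "an expected CR rate of 50% in MA/metformin group", "with a power of 0.9 at a two-sided significance level of 0.05". The normal approximation gives 77 per arm (154) with pooled variance and 74 per arm (148) with unpooled variance, before any allowance for loss. So 150 is reproduced to within 3%. It does not depend on the time-to-CR method.

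**Inputs for the check.** The 3-month CR rates of 25% and 50% come from the plan. The later CR rates and all stop rates are assumptions. A stop here means progression, or a side-effect stop after which CR does not occur or is not counted.

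**Formulas.** Take four 3-month intervals. Let c be the proportion of women still on treatment who reach CR in an interval, and s the proportion of the remainder who then stop.

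- Women at risk at the next interval = current risk × (1 − c)(1 − s).
- Cumulative incidence of CR = sum of (risk × c).
- One minus Kaplan-Meier, with stops censored = 1 − product of (1 − c).

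**Case 1: equal CR (c = 25% throughout), stopping 2% (MA) vs 8% (MA plus metformin).**

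- MA: 0.75 × 0.98 = 0.735; incidence = 0.25 × (1 + 0.735 + 0.5402 + 0.3971) = 66.8%.
- MA plus metformin: 0.75 × 0.92 = 0.69; incidence = 0.25 × (1 + 0.69 + 0.4761 + 0.3285) = 62.4%.
- One minus Kaplan-Meier, both arms: 1 − 0.75⁴ = 68.4%.
- Excess: 1.5 and 6.0 points. A true 4.4-point deficit disappears from the curves.

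**Case 2: the plan's 3-month rates, stopping 3% vs 6%.** MA has c = 25% throughout; MA plus metformin has c = 50%, 30%, 25%, 25%.

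- MA: 0.75 × 0.97 = 0.7275; incidence = 0.25 × (1 + 0.7275 + 0.5293 + 0.3850) = 66.0%; one minus Kaplan-Meier 68.4%; excess 2.3 points (0.6836 − 0.6604, before rounding).
- MA plus metformin: risk sets 1, 0.47, 0.3093, 0.2180; incidence = 0.5 + 0.141 + 0.0773 + 0.0545 = 77.3%; one minus Kaplan-Meier = 1 − 0.5 × 0.7 × 0.75 × 0.75 = 80.3%; excess 3.0 points.
- Between-arm difference: 11.2 points true, 12.0 points by Kaplan-Meier. The shift is 0.7 points before rounding.

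**Cross-check with constant hazards.** Let p be the true CR proportion and s the share of all women stopped by month 3. With H = −ln(1 − p − s) and H_CR = H·p/(p + s), one minus Kaplan-Meier at month 3k is 1 − exp(−k·H_CR), and the true incidence is p/(p + s) × (1 − exp(−k·H)).

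| p, s at month 3 | 3 months: true vs 1 − KM | 12 months: true vs 1 − KM |
|---|---|---|
| 25%, 5% | 25.0% vs 25.7% | 63.3% vs 69.5% |
| 50%, 5% | 50.0% vs 51.6% | 87.2% vs 94.5% |
| 25%, 10% | 25.0% vs 26.5% | 58.7% vs 70.8% |
| 50%, 10% | 50.0% vs 53.4% | 81.2% vs 95.3% |

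With no stops the two estimates agree. The excess grows with the stop rate. For a given share of women stopped by month 3, it also grows with the CR rate.

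**The case against.** The strongest reply is that the plan does not say these women are censored. Kaplan-Meier is compatible with a sound analysis: women who stop can stay in the risk set as not having reached CR until month 12, and the excess vanishes. This stands. Censoring at the stop is usual practice, not stated text, so the overstatement is conditional on it. But nothing in the plan steers the analyst away from that practice.

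Four stronger readings are tempting, and the documents do not support them:

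- *The curve is bound to contradict the 6-, 9- and 12-month CR rates.* The plan gives no denominator for those rates. They can differ from the curve if stopped women count there as non-responders.
- *The bias is always largest in the arm with more stops.* The CR rate matters too. At 3 months, 50% CR with 5% stops gives an excess of 1.6 points, and 25% CR with 10% stops gives 1.5. That the added drug causes more stops is plausible but undocumented.
- *A side-effect stop rules out CR.* The plan says what ends treatment, not what ends assessment. Such a woman might reach CR later, and whether that counts is a choice the plan has not made. The case is strongest for progression.
- *The primary result is at risk.* Time to CR is secondary, no between-arm test is named for it, and nothing says any CR rate is read from the curve.

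It is also fair to say that the 4.4-point figure needs equal CR and a fourfold difference in stopping. With the plan's own 3-month rates and twofold stopping, the comparison moves by only 0.7 points.

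**Conclusion.** The point holds as a conditional weakness in a secondary analysis. The plan names two ways treatment ends without CR and applies Kaplan-Meier to time to CR without saying how those women are handled. If they are censored at the stop, one minus Kaplan-Meier is at or above the cumulative incidence of CR in each arm. This is a mathematical property once CR after a stop is absent or not counted; only the size is uncertain.

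Under the interval assumptions (2% to 8% of non-responders stopping every three months), the 12-month excess is about 1.5 to 6 points per arm and the between-arm distortion 0.7 to 4.4 points. Under constant hazards with 5% of all women stopped by month 3, the 12-month excess is 6 to 7 points; with 10%, it is 12 to 14. If stops are rare it is small. None of these stop rates comes from the documents. A better estimator is available at almost no cost, so the plan should be changed.

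**What to change.** Revise the time-to-CR text in Statistical analysis as follows:

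1. Estimate time to CR by the cumulative incidence function (Aalen-Johansen), with progression before CR as a competing event.
2. State whether CR after a side-effect stop counts. If it does, continue to assess these women and count it. If it does not, treat the stop as a competing event.
3. Censor only women lost to follow-up or reaching the end of follow-up.
4. If the analysis must stay within SPSS, keep women with a competing event in the Kaplan-Meier risk set as not having reached CR to month 12.
5. State the denominator for the 3-, 6-, 9- and 12-month CR rates. If women with a competing event count there as non-responders, the curve and the rates will agree apart from losses.

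The cost is a few sentences and a censoring-date rule, plus continued assessment after side-effect stops if the sponsor decides that later CR counts. The reported CR curve will be slightly lower. The primary end point and the sample size of 150 do not change.
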